#### **g. Available Population**

With all NRN Centers enrolling into the observational study (which also excluded those with major congenital heart disease, acute hypotension resulting directly from known acute maternal and/or fetal hemorrhage within 24 hours prior to delivery, pituitary hypoplasia, congenital adrenal hyperplasia, or known chromosomal disorder), ~100-115 mechanically ventilated infants in this gestational age range are admitted to NRN Centers each month and 25% of these received inotropes (21% if exclude encephalopathy, CDH, and omphalocele and those who receive cooling for HIE). We, therefore, anticipate ~22 to 25 eligible infants each month.

Infants in the same age group within the NRN with hypoxic ischemic encephalopathy may be eligible for the ongoing cooling studies in the NRN. However, infants who are cooled or have HIE will be ineligible for this study.

#### **h. Estimated Recruitment Time**

With 60% consent, 48 months would be needed to enrollment goal. Anticipating delays in startup and missed infants, study enrollment should be completed in a little over four years.

### **8. Risks and Benefits**

**Short-term adverse events.** The following will be reported within 72 hours of diagnosis and 24 hours of discovery:

- **Mortality.** No study of hydrocortisone therapy in newborns or in other critically ill populations has shown an increase risk in mortality, and some have shown decreased risk of death. This study population is at high risk of death from the underlying diseases (1.2%–11%).
- **Late-onset ( $\geq 5$  days) culture-confirmed infection.** Recent large randomized controlled trials in adults and preterm newborn infants showed no increased risk of infection from 7–14 days of glucocorticoid treatment. However, culture-proven late onset infection will be tracked and reported. Early and late onset culture-proven infection in this population is 1.4% and 4.2% respectively (Vermont Oxford Network 2009). Anticipated incidence <4.2%.
- **Gastrointestinal perforation.** In contrast to the extremely low birth weight infant where the incidence of spontaneous intestinal perforation is 4%, this patient population is

developmentally more mature and should not be at risk for this event, particularly since these patients will not be simultaneously exposed to indomethacin.

- **Hypertension.** These infants are often on inotropes, which often cause high blood pressure by themselves. Glucocorticoids' actions are to increase blood pressure. It is unknown if the combination of these two therapies results in a higher occurrence of hypertension. This will be tracked by counting the number of 12-hour periods in which the blood pressure was higher than 95th percentile for weight and age and the receipt of any antihypertensive medication. Incidence is unknown.
- **Hyperglycemia.** Higher dose glucocorticoids can raise blood glucose levels acutely and for short periods of time (hours), without long-term consequences. No study to date has shown a need for insulin secondary to glucocorticoid administration for the treatment of hypotension. Data on the use of insulin will be collected if administered during the study drug time and when glucose is >180mg/dl on at least two determinations at least 6 hours apart. Anticipated incidence <1%.

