**Table 3. Systolic, diastolic, and mean blood pressures at time of initiation of therapy. Mean (SD).**

	First fluid bolus		First vasopressor dose		First steroid dose	
	<37 wks GA N = 168	≥37 wks GA N = 324	<37 wks GA N = 66	≥37 wks GA N = 149	<37 wks GA N = 30	≥37 wks GA N = 73
Systolic BP	53.3 (10.7)	58.8 (14.3)	47.9 (8.5)	52.7 (12.5)	49.2 (13.1)	55.2 (13.0)
Diastolic BP	30.5 (13.0)	43.2 (10.9)	29.5 (15.1)	31.4 (10.3)	32.2 (10.8)	36.1 (9.4)
Mean BP	38.4 (9.8)	42.4 (11.8)	35.6 (7.7)	39.1 (10.1)	39.1 (11.2)	43.4 (10.3)

**Table 4. Therapy received for cardiovascular insufficiency; timing, blood pressure at time of initiation and total days of therapy. Median (25th percentile, 75th percentile); % (n/N)**

	All N = 502	Volume expanders N = 488	Inotropes N = 215	Steroids N = 103
Age at 1 st dose (hours)	4.0 (1.2, 15.1)	3.5 (1.1, 14.8)	12.633 (5.03, 24.7)	26.2 (12.4, 43.5)
Mean BP at 1 st dose	39 (33, 47)	39 (33, 47)	36 (31, 42)	41 (35, 49)
% with mean BP <PMA	39.2% (131/334)	39.8% (137/344)	53.8% (93/173)	32.6% (30/92)
Total Days	NA	NA	2.5 (1, 5)	4 (2, 7)

The timing of therapy is outlined above in Table 4. Most infants had therapy initiated for cardiovascular insufficiency within the first 24 hours of age.

Low blood pressure was not the only clinical measure used to initiate therapy for cardiovascular insufficiency and appears to be an unreliable measure. Therefore, the presence of inotropes was used to evaluate outcomes. The patient characteristics and outcomes are listed in Tables 5 and 6. Outcomes were significantly worse in those who received inotropes vs. those who did not.

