receptors by higher cortisol concentrations. Therapy with active drug or placebo should be instituted ideally within 12-24 hours of initiation of inotrope therapy. All other treatments will be at the discretion of the clinical care team. This real-world management design will increase generalizability of study results and improve compliance with study procedures.

*Rationale for hydrocortisone dosing: see section 6, Background, for rationale on dosing.*

**Laboratory.** One blood sample (1ml) for a cortisol level will be obtained within 4 hours prior to initiation of study drug for each enrolled patient. The sample of blood from each center will be labeled study patient ID and shipped to a central laboratory (The University of New Mexico CTSC Research Lab) in Albuquerque, New Mexico. The cortisol levels will be measured by the IMMULITE 1000 cortisol procedure (chemiluminescent system).

Blood for cortisol levels is not mandatory for study if parents wish to decline blood draw for this timed study lab. Cortisol levels obtained by clinical team will be collected from medical chart. The relationship between cortisol concentrations and response to hydrocortisone, severity of illness and outcomes will be analyzed.

The literature shows conflicting results on the value of cortisol concentrations in determining therapy. Infants often respond to glucocorticoids regardless of cortisol levels. While we found that infants with cortisol values <15 mcg/dl had positive responses to hydrocortisone in a small retrospective study, other studies were unable to use cortisol values to predict the severity of illness, need for cardiovascular support, or the response to treatment.

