Serious adverse events to be reported to NICHD within 24 hours include death, late onset sepsis, hyperglycemia receiving insulin, hypertension receiving antihypertensive medication or intestinal perforation with an assessment as best as possible as to the cause of the perforation (NEC, spontaneous, other).

b. Interim safety monitoring

The DSMC will compare the incidence of death and a composite of serious adverse events including death, late onset sepsis, intestinal perforation, and hyperglycemia requiring insulin between the two treatment arms after every 100th infant reaches status (death, discharge, transfer or 60 days of age). Since 646 infants are to be enrolled in this trial, this will involve interim looks approximately once every 9 months, or after the enrollment of every additional 160 infants, giving a Pocock boundary of 2.413, with a corresponding significance level of  $p<0.0158$  (Pocock, 1977). Such reports will be forwarded to the Chair of the DSMC when there is any suggestion of a trend towards a difference between the two treatment arms emerging. They will also be made available to the full DSMC at their scheduled meetings after 50% and 75% of the trial infants reach status as defined by the GDB. Interim efficacy analysis using O'Brien-Fleming stopping bounds will also be made available to DSMC when 50% of primary outcome data is available.

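### Infection is a named safety event only when late-onset (5 days or later, clock not stated), so non-fatal culture-proven infections after the first dose but before day 5 are not counted as infections

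*Combined protocol and SAP*

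**What the plan says.** Section 8 (Risks and Benefits) lists the short-term adverse events. Its infection item is "Late-onset ( $\geq 5$ days) culture-confirmed infection", and the stated commitment is that "culture-proven late onset infection will be tracked and reported". The same item gives background rates for both kinds of infection: "Early and late onset culture-proven infection in this population is 1.4% and 4.2% respectively". It does not say whether the 5 days are counted from birth or from the first dose.

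The DSMC Safety Monitoring text then uses the term twice:

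- For expedited reporting: "Serious adverse events to be reported to NICHD within 24 hours include death, late onset sepsis", followed by the metabolic, blood pressure and perforation items.
- For the interim comparison between arms: a "composite of serious adverse events including death, late onset sepsis, intestinal perforation, and hyperglycemia requiring insulin". The 5-day cut-off is not repeated in either place.

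No other part of the plan fills the gap. The monitored events under DSMC item a name hyperglycemia, hypertension and gastrointestinal perforation, but no infection. Table 9 (short-term outcomes) has necrotizing enterocolitis but no sepsis row. Aim c compares adverse events as the protocol defines them, so it inherits the same limit.

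On timing, Section 7c says that study drug "should be instituted ideally within 12-24 hours of initiation of inotrope therapy". Section 6b reports from the observational cohort that "Most infants had therapy initiated for cardiovascular insufficiency within the first 24 hours of age".

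**The concern.** The plan treats infection as a possible harm of the study drug: it sits in the adverse-event list, in the serious-event list and in a composite tested against a Pocock boundary. A safety event of that kind would normally be counted from first exposure. Here the counter opens at a fixed day 5, while most infants are expected to start treatment on the first or second day after birth. The uncounted interval is also the part of the course with the highest daily dose. The DSMC and the Aim c comparison would see only part of the on-treatment infection experience, and nothing in the plan obliges anyone to tabulate the rest by arm. Because the clock is undefined, two sites could also classify the same infection differently.

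**Working it through.** **Inputs**

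- Dose list, Section 7c: 1 mg/kg load; 0.5 mg/kg every 6 h × 12; 0.5 mg/kg every 12 h × 4; 0.5 mg/kg once.
- Age at first inotrope, Table 4: median 12.6 h (quartiles 5.0 and 24.7 h).
- Target delay from inotrope to study drug, Section 7c: 12-24 h.
- Latest age at randomization, Section 7b: 96 h.
- Background infection rates, Section 8: early 1.4%, late 4.2%.
- Planned enrollment, Section 7e: 646.

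**Step 1. Reproduce the plan's schedule.** Place the load at 0 h, the 6-hourly doses at 6-72 h, the 12-hourly doses at 84, 96, 108 and 120 h, and the last dose at 144 h. The daily totals are 2.5, 2, 2, 1, 1, 0.5 and 0.5 mg/kg, as Section 7c states. The sum is 1 + 6 + 2 + 0.5 = 9.5 mg/kg.

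**Step 2. Typical age at first dose.** 12.6 + 12 = 24.6 h and 12.6 + 24 = 36.6 h, so about 25-37 h.

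**Step 3. Part of the course before the cut-off, if it is 120 h of age.** Hours missed = 120 − age at first dose. Dose share = mg/kg due before that time ÷ 9.5.

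| Age at first dose | Hours before cut-off | Dose by then (mg/kg) | Share of total dose |
|---|---|---|---|
| 24.6 h | 95.4 | 7.5 | 79% |
| 36.6 h | 83.4 | 7.0 | 74% |
| 48.7 h (upper quartile + 24 h) | 71.3 | 6.5 | 68% |
| 72 h | 48 | 4.5 | 47% |
| 96 h | 24 | 2.5 | 26% |

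For the typical start, 83.4/168 = 50% and 95.4/168 = 57% of the 7-day course comes before the cut-off, that is, about 3.5-4 days. The first half of the course (84 h) lies wholly before the cut-off only if drug starts by 120 − 84 = 36 h of age.

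**Step 4. Other readings of the clock.**

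- Day 5 begins at 96 h of age: the shares are 68% (start 24.6 h), 58% (36.6 h), 26% (72 h) and 0% (96 h).
- Five days from first dose: 8.5/9.5 = 89% for every infant.

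**Step 5. Events at the plan's background rates.** Late-onset: 646 × 0.042 = 27.1. Early-onset: 646 × 0.014 = 9.0. Total 36.2, of which early-onset is 9.0/36.2 = 25%. The 9 is an upper bound on what the definition misses: some early-onset infections will be present before the first dose, and the documents give no split. These are background rates and say nothing about the size of any drug-related excess.

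**The case against.** The strongest reply is that the restriction is a reasonable trade of sensitivity for specificity. Treatment starts within days of birth, so a positive culture before day 5 may reflect infection already present at randomization. Adding such events to both arms would dilute the contrast in a composite that carries a stopping boundary. This stands, and it is a good reason not to replace the late-onset component of the composite. It is not a reason to leave post-dose early infections untabulated.

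Three further points limit the concern:

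- **Dose share is not event share.** An infant who has received three quarters of the drug by day 5 is still observed for infection afterwards, so the counted events arise in exposed infants. A reader might infer that a drug-related excess would go unseen. The documents do not support that: on their own rates most infections, about 27 of 36, are late-onset and counted.
- **A reader might infer that infections in the first half of the course are never counted, or that only the tail of the course is observed.** Neither holds in general. With a cut-off at 120 h of age, starts at 72-96 h lose only the first one to two days. Even for the typical start, 43-50% of the course remains, and the interim status definition (death, discharge, transfer or 60 days of age) runs well past it. A fatal early infection enters the composite as a death.
- **The start times are assumed.** The 12-24 h delay is a target. The Table 4 cohort included infants whom this trial excludes; in Table 5, 22.2% of the inotrope group were cooled. Later starts shrink the gap.

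It can also be said that the lists are introduced by *including* and so are not exhaustive. That carries little weight for a composite tested at p<0.0158, which needs a fixed list of components, and the only infection named is late-onset.

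**Conclusion.** The gap is real and moderate in size. As written, a non-fatal culture-proven infection with onset after the first dose and before day 5 is not counted as an infection in the adverse-event list, the serious-event list, the DSMC composite or Aim c. For an infant starting at about 25-37 h of age, this leaves out roughly the first 3.5-4 days and 74-79% of the dose, if day 5 means 120 h of age. The share falls to 47% and 26% for starts at 72 h and 96 h. A clock from 96 h of age gives less, and a clock from first dose gives more. In events, at most about 9 of about 36 expected infections are affected at background rates.

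The result rests on the observational cohort's inotrope timing, on the target delay being met, and on the Section 8 rates applying to this population. The absence of any other infection term, and of a stated clock, rests on the text alone. The point warrants an amendment because the exposure period is the one a safety count should cover and the change is small. It does not show that the interim monitoring is invalid.

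**What to change.** 1. In Section 8, state the clock for the 5-day cut-off, and use the same definition wherever late-onset sepsis appears in the DSMC text.
2. Add to the adverse-event and serious-event lists any culture-confirmed infection whose first positive culture is drawn after the first dose of study drug, excluding organisms already cultured before that dose.
3. Report this event by arm to the DSMC and in the Aim c comparison, split into before day 5 and from day 5 onward.
4. Keep late-onset sepsis as the existing composite component, and show the composite with all post-dose infections as an additional comparison.

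The cost is wording in Section 8 and its DSMC text, plus collection of culture date and time, which should be available from the chart. Some perinatally acquired infections that declare themselves after the first dose will be counted in both arms; the split at day 5 and the unchanged composite keep them visible without diluting the monitored contrast. No dose, schedule or treatment rule is affected.

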### **Other Potential issues**

- **Adrenal suppression.** Even in the most premature infants, this brief period of therapy has not previously been associated with adrenal suppression. If any infant shows signs consistent with adrenal insufficiency after discontinuation of the study drug (hypotension, oliguria, hyponatremia, hyperkalemia), a blood sample can be sent for cortisol and therapy with hydrocortisone reinstated if deemed necessary by the clinical care team.
- **Neurodevelopmental deficits.** The neurodevelopmental benefits or risks of using hydrocortisone for the treatment of cardiovascular insufficiency is unknown. This RCT will be an important addition to the literature regarding long-term risks/benefits of this therapy. No previous study has shown adverse neurodevelopmental effects of hydrocortisone treatment in the newborn period in extremely low birth weight infants. Because this study population is more mature, it is even less likely to adversely impact this proposed study population; however, our study design will enable us to evaluate that issue.
- **Persistent hypotension.** Infants will be treated in the routine manner by the attending clinicians in their respective centers to allow real-world design. Open-label hydrocortisone is discouraged but if given, the recommended plan is listed in the methods section above. Data on infants who receive open-label hydrocortisone will be collected and/or on infants who receive 3 different types of inotropes or more.

### **Data Safety and Monitoring Committee (DSMC) Safety Monitoring.**

#### a. Adverse events to be monitored

Adverse events to be monitored will be those previously associated with glucocorticoid therapy, including hyperglycemia, hypertension and gastrointestinal perforation. Any infant who develops new, sustained hyperglycemia (>180mg/dl on at least two determinations at least 6 hours apart or receiving insulin) or new, sustained hypertension (mean arterial pressure >95th percentile for age on four serial determinations over at least 12 hours or receiving antihypertensive) may have study drug held or discontinued if, in the opinion of the attending neonatologist, there is no plausible alternative explanation for these findings (such as new thrombus). Not enrolling very preterm infants and excluding infants receiving indomethacin/ibuprofen should minimize the possibility for spontaneous GI perforation. These short term adverse events as defined here, should be reported within 24 hours of discovery to PI.

Also similar to the NRN hydrocortisone extubation trial, we will also specifically monitor for signs of adrenal insufficiency for 3 days after study drug is discontinued, including hypotension and oliguria, as well as hyponatremia and hyperkalemia on clinically obtained electrolyte specimens. Signs of adrenal insufficiency within 3 days after study will be reported within 24 hours of discovery. Previous studies of hydrocortisone at various doses have not reported these signs after discontinuation of a tapering course of the drug.

Patients who develop hypotension and oliguria (shock) significant enough in the judgment of the attending neonatologist to require support with volume and/or vasopressors may have a clinically indicated blood sample drawn for cortisol and may be restarted on hydrocortisone or other therapy for shock at the discretion of the clinical attending. Open-label hydrocortisone should be given at a test dose of 1mg/kg, with continuation of the therapy based on clinical response to the first dose. Persistent hypotension despite inotrope therapy and study drug will be treated per the routine of each center as directed by the treating clinician. Open-label hydrocortisone use will be considered a protocol deviation and it will be reported to DSMC if this deviation occurs in more than 20% of those enrolled.

Serious adverse events to be reported to NICHD within 24 hours include death, late onset sepsis, hyperglycemia receiving insulin, hypertension receiving antihypertensive medication or intestinal perforation with an assessment as best as possible as to the cause of the perforation (NEC, spontaneous, other).

b. Interim safety monitoring

The DSMC will compare the incidence of death and a composite of serious adverse events including death, late onset sepsis, intestinal perforation, and hyperglycemia requiring insulin between the two treatment arms after every 100th infant reaches status (death, discharge, transfer or 60 days of age). Since 646 infants are to be enrolled in this trial, this will involve interim looks approximately once every 9 months, or after the enrollment of every additional 160 infants, giving a Pocock boundary of 2.413, with a corresponding significance level of  $p<0.0158$  (Pocock, 1977). Such reports will be forwarded to the Chair of the DSMC when there is any suggestion of a trend towards a difference between the two treatment arms emerging. They will also be made available to the full DSMC at their scheduled meetings after 50% and 75% of the trial infants reach status as defined by the GDB. Interim efficacy analysis using O'Brien-Fleming stopping bounds will also be made available to DSMC when 50% of primary outcome data is available.

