## 3. Hypothesis

We hypothesize that therapy with hydrocortisone will ameliorate the clinical syndrome of cardiovascular insufficiency syndrome seen in many critically ill term and late preterm infants, thereby decreasing short- and long-term morbidity and mortality.

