## 4. Specific Aims

**Goal of study.** Although short term use of hydrocortisone is believed to be safe (see Table 1), evidence is limited to support its use in treating hypotension in the critically ill term and late preterm infant. **Despite this paucity of data, many infants are increasingly receiving glucocorticoids for cardiovascular insufficiency**—13.1% of intubated and mechanically ventilated infants in our own preliminary observational NRN data and 13.5% in a recent report of infants with meconium aspiration syndrome. We propose to **perform a RCT of hydrocortisone** for the treatment of cardiovascular insufficiency in critically ill, term and late preterm newborn infants who are mechanically ventilated in their first 72 postnatal hours. Our

goal is to determine if hydrocortisone treatment improves cardiovascular function, ameliorates other short-term outcomes, and increases survival without neurodevelopmental impairment.

**Specific aims** of this multicenter, randomized, masked, placebo-controlled trial within the NRN are:

- a. Compare the incidence of death or neurodevelopmental impairment at 22-26 months in critically ill, mechanically ventilated, term and late preterm newborn infants receiving inotropes for cardiovascular insufficiency in the first 72 hours of age treated with 7 days of hydrocortisone vs. placebo. We **hypothesize** that hydrocortisone will decrease the incidence of death or neurodevelopmental impairment in these infants compared to placebo.
- b. Compare short-term outcomes between infants treated with hydrocortisone vs. placebo including duration of mechanical ventilation and oxygen therapy, days to full feeding, and length of hospital stay. We **hypothesize** that infants who receive hydrocortisone will spend fewer days on mechanical ventilation and oxygen, will take fewer days to reach full enteral feeds, and will have shorter stays in the hospital.
- c. Compare adverse events (defined below) between infants treated with hydrocortisone vs. placebo. We **hypothesize** that adverse events will not occur at a higher rate in those receiving hydrocortisone compared to placebo.

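### No bounded interim safety comparison isolates non-fatal steroid harms: the DSMC composite includes death, so a survival gain could largely mask them

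*Combined protocol and SAP*

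**What the plan says.** Section 8, DSMC Safety Monitoring, part b (Interim safety monitoring), names two between-arm comparisons. One is death. The other is "a composite of serious adverse events including death, late onset sepsis, intestinal perforation, and hyperglycemia requiring insulin". The threshold follows in the same paragraph, "giving a Pocock boundary of 2.413", with a nominal level of 0.0158. The looks are described both as every 100 infants reaching status and as "approximately once every 9 months, or after the enrollment of every additional 160 infants".

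The expected direction for death is downward. Section 3 expects hydrocortisone to ameliorate cardiovascular insufficiency, "thereby decreasing short- and long-term morbidity and mortality". Aim a of section 4 hypothesises that "hydrocortisone will decrease the incidence of death or neurodevelopmental impairment in these infants compared to placebo".

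Non-fatal events are handled elsewhere too. Aim c compares adverse events between arms. Part a of the DSMC section lists hyperglycemia, hypertension and gastrointestinal perforation for monitoring. The end of the adverse-event text requires the serious events to be reported individually to NICHD within 24 hours. None of these sets an interim between-arm threshold.

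**The concern.** The composite is the only bounded comparison that includes the non-fatal steroid harms, and it adds them to an outcome that the trial expects to improve. If hydrocortisone saves lives and also causes infection, perforation or insulin-treated hyperglycemia, the two effects pull the composite in opposite directions. If it does not change mortality, deaths in both arms add events that carry no information about toxicity. Either way, a real excess of non-fatal harm is less likely to reach the threshold than it would be if those events were compared alone. At stake is how soon the DSMC gets a formal signal of steroid toxicity, not the primary analysis.

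**Working it through.** **The plan's own figure.** The Pocock constant for a two-sided 5% level, by recursive numerical integration with equally spaced looks, is 2.361 for four looks, 2.413 for five and 2.453 for six. At 2.413 the nominal level is 2 × (1 − Φ(2.413)) = 0.0158. The plan's figures are therefore the five-look values, and five looks are used below.

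**Inputs**
- Total 646 infants, 1:1 (sections 7a and 7e): 323 per arm, with looks at about 65, 129, 194, 258 and 323 per arm.
- Control death *d*. Table 6-2 pooled: (0.143 × 42 + 0.098 × 93) / 135 = 15.12 / 135 = 11.2%. Section 8 gives 1.2%-11%, so 5% and 1.2% are also shown. Table 6-1 gives 15.7%, but that table still includes infants with diaphragmatic hernia and cooled infants, whom the trial excludes, so it is an upper case.
- Non-fatal serious events *e*. Section 8 gives 4.2% late-onset infection ("Anticipated incidence <4.2" percent) and under 1% hyperglycemia; perforation has no figure for this population. Assumed: 4.2% + 1% = 5.2%, doubled to 10.4% under hydrocortisone.
- Death relative risk (RR). The plan states none. Assumed: 1, 0.8 and 0.67; the last is the planning value in section 7e for death or impairment.

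**Composite rate** = *d* + (1 − *d*) × *e*, components independent.
- *d* = 11.2%: placebo 0.112 + 0.888 × 0.052 = 15.8%. Hydrocortisone, RR 1: 0.112 + 0.888 × 0.104 = 20.4%; RR 0.8: 0.0896 + 0.9104 × 0.104 = 18.4%; RR 0.67: 0.075 + 0.925 × 0.104 = 17.1%.
- *d* = 5%: placebo 9.9%; hydrocortisone 14.9% (RR 1), 13.4% (RR 0.67).

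Death's share of placebo composite events is *d* divided by the composite rate: 0.112 / 0.158 = 71%; 0.05 / 0.099 = about 50%; at 1.2%, 0.012 / (0.012 + 0.988 × 0.052) = 0.012 / 0.063 = 19%.

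**Chance of ever crossing for harm.** At each look z = (p_T − p_C) / √(2 p̄(1 − p̄)/n); crossing means z > 2.413 at any of the five looks; 20,000 simulated trials per scenario.

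| Control death | RR 1 | RR 0.8 | RR 0.67 |
|---|---|---|---|
| 15.7% (upper case) | 20-21% | 6% | 2% |
| 11.2% | 25% | 11% | 5% |
| 5% | 38-39% | 27% | 22% |
| 1.2% | 53% | – | 48% |

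Non-fatal events alone cross in about 59-60% of trials if independent of death. If only survivors can have them, the range at 5% and 11.2% control death is about 53-60%. If they start at 2.5% and double to 5%, it is only about 25-28%.

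**When cancellation is complete.** Setting the two composite rates equal gives a treated death rate of 1 − (1 − *d*) × 0.948 / 0.896. At *d* = 11.2% this is 6.0%, an RR of about 0.54. At 15.7% it is 10.8%, an RR of about 0.69. At 5% it is negative, so no survival gain could cancel the harm completely.

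**The remedy tested** (crossing for harm on any bounded comparison, control death 11.2%)

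| Scenario | Plan as written | Replace composite by non-fatal only | Add non-fatal comparison |
|---|---|---|---|
| No effect on anything | 4% | 5% | 6% |
| Non-fatal doubled, death RR 0.67 | 5% | 59% | 59% |
| Death and non-fatal both up by half | 62% | 52-55% | 63-65% |

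**The case against.** A reader might infer that death in the composite cancels the steroid harms, so that the boundary cannot detect them. The documents do not support that. Complete cancellation needs a particular survival gain and is impossible at 5% control mortality under these inputs. With no mortality effect there is dilution only, and larger harms still cross: with non-fatal events tripled and a death RR of 0.67, re-calculations give 37-41% at 11.2% control death.

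Nor do the documents support saying that non-fatal harms are never compared between arms, since Aim c does so at trial end. Serious events also reach NICHD individually. Death is shown separately at every look, so the DSMC could see mortality pulling on the composite. Reports go to the DSMC Chair at any suggestion of a trend, a looser trigger than 2.413, and the plan reserves the term stopping bounds for the efficacy analysis. All this stands, and it means that crossing probability understates what an alert committee might notice. It does not close the gap: single-case reports have no comparator, the trend trigger is read from the same diluted composite, and nothing formal addresses the non-fatal events by themselves.

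The inputs are also open to challenge. Section 8's mortality range runs well below 11%, and the loss shrinks there. The infection and hyperglycemia rates are upper limits, and lower rates weaken the non-fatal comparison too. Both points stand and are why ranges are shown.

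Finally, it is tempting to conclude that death should simply be removed from the composite at no cost. That is wrong: if death and non-fatal events rise together, pooling them helps, and replacing the composite lowers detection from about 62% to 52-55%.

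**Conclusion.** The point holds in a limited form. No bounded interim comparison isolates the non-fatal serious events, and including an outcome expected to fall weakens the one comparison that contains them. For a doubling of non-fatal events at about 11% control mortality, detection drops from roughly 53-60% to about 25% with no mortality effect, and to 5-11% with a death RR of 0.67-0.8. At 5% mortality the loss is moderate, and at 1.2% it is small.

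These figures rest on assumed death relative risks, on a 5.2% non-fatal rate built from upper limits, on independence of the components, and on five equal looks. The plan's text could also be read as about four or six looks; a six-look run with near-identical inputs gave the same picture (5.6% against 53% at 11.2% mortality and RR 0.67). This is a worthwhile improvement to the monitoring plan, not an error that must be corrected before the trial can be relied on.

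**What to change.** In section 8, Interim safety monitoring, keep the death comparison and the existing composite. Add, at each look, a between-arm comparison of the proportion of infants with any non-fatal serious event (late-onset sepsis, intestinal perforation, hyperglycemia requiring insulin), under the same boundary and read alongside death, because early deaths remove infants from risk of later events. Specify it before the first look.

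The cost is one sentence, one more DSMC table, and a rise in the chance of a false alarm in the harm direction from about 4% to 6%. Sample size, treatment and the primary analysis are unaffected. Adding rather than replacing keeps the composite's sensitivity when death and non-fatal harm move together.
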